### **1.1 Study Setting**

The ASPIRE study is an uncontrolled observational feasibility study, and a collaboration between the University of South Wales and Cwm Taf Morgannwg University Health Board (CTMUHB). The study is based at Ysbyty Cwm Rhondda (YCR) and Keir Hardie

Primary Care (KHPC) centres, where participant recruitment will take place. Study participants will be invited to provide capillary blood samples (via finger prick sampling) for testing. The principal investigators are [name] at YCR and [name] at KHPC. Upon clinical assessment, and after provision of consent, participants will undergo an ARI (acute respiratory infection) POC assay. This is a dual marker immunoassay designed to detect raised levels of C-reactive protein and MxA in capillary blood. The assay uses the sensitivity of CRP and specify of MxA to aid in the differentiation of ARI's in Primary Care.

The POC assay results will be compared to the participants' clinical outcomes and the physician directed treatment pathway via reviewing medical records and by contacting the patient from 14 days after their visit.

The study is funded by a KESS award.

## 2. Introduction

### 2.1 Lay Summary

Antibiotic stewardship is fast becoming an essential measure to improve antibiotic prescribing by clinicians. Antibiotic stewardship not only presents a cost-effective strategy for the NHS but addressed the issue of antimicrobial resistance (AMR) and protects patients from harm caused by unnecessary antibiotic use.

The economic costs of antibiotic resistance are largely unknown, but it is anticipated that with an increased number of cases, effects to the economy could be severe. Infections and infectious diseases cost England & Wales an estimated £30 billion a year, with many cases of acute respiratory infections (Chaplin, 2017). POC diagnostic tests in a clinical setting could give clinicians the ability to distinguish between microbial and viral infections, providing a more informed decision to antibiotic prescribing.

The purpose of this study is to safely distinguish between bacterial or viral respiratory infections in a primary care setting using "point of care" (POC) testing to provide a retrospective insight as to whether clinical assessment of an acute respiratory infection (ARI) is justified. Upon clinical assessment, the current clinical practice prescribes antibiotics based on symptoms reported by the patient and a subjective review by the GP. This results in antibiotics being prescribed from an informed decision made by the clinician, based only from patient symptoms. The use of a dual marker immunoassay could guide informed decisions based on qualitative data and degree of infection using POC testing in Primary Care.

The POC assay uses a dual marker immunoassay to differentiate between a viral and bacterial infection. C-reactive protein (CRP) is raised in the blood stream in response to inflammation. CRP can be elevated in viral infections, but generally the rise is to higher levels in bacterial infections, especially severe bacterial infections. Another blood protein, the MxA protein, is selectively increased in people with viral infections and therefore has the potential to greatly enhance the rapid distinction between viral and bacterial respiratory infections.

NICE guidance from 2014 recommends the use of CRP POC test in the diagnosis and appropriate management of lower respiratory tract infections in adults aged 18 and over (excluding people with COPD) after clinical assessment whether antibiotics should be prescribed. The study POC assay data could be used as an effective tool alongside NICE guidelines to prescribe antibiotics based on CRP concentration where an infection may be viral. Recent clinical studies suggest the POC test is highly effective, yielding over 80% sensitivity and over 90% specificity when identifying bacterial and viral infections in adults (NICE, 2020).

## 2.2 Background

Respiratory tract infections (RTI) are a frequent health problem in developed countries, and the third most common cause of medical referral worldwide. Acute respiratory infections (ARI's) account for most antibiotic prescriptions written and around 20% of all medical referrals in developed countries (Reed, 2015). Data from 88 countries in five continents, with a total population of nearly 1200 million, showed that deaths due to bacterial and viral ARI's in 1972 amounted to 666 000 (A. Bulla, 2021).

ARI's pose a problem for clinicians due to their overlapping profiles of signs and symptoms. Clinical uncertainty regarding a suspected ARI patient's infection aetiology along with patient expectation can frequently result in the prescription of antibiotics even when it is probable that an infection is viral (Davies, 2016). The unnecessary use of antibiotics can have negative consequences, including the spread of antibiotic resistance, which poses a global health threat.

The rise of antibiotic resistance (AR) in the NHS has resulted in the number of infections due to antibiotic-resistant bacteria rising dramatically. The uptake of antibiotics as a population along with how they are used by a patient, has shown to be proportional to the prevalence of AR (Goossens, Ferech, Vander Stichele and Elseviers, 2005). The effects of wrongly prescribing antibiotics unnecessarily expose patients to the risk of adverse events caused by AR, such as Stevens-Johnson syndrome and *Clostridium difficile* infection (Tandan et al., 2017). The magnitude of these adverse outcomes are more pronounced as disease severity, strain virulence, or host vulnerability increase. The cost of treatment delays and failure to patients in healthcare systems incur the greatest negative impact of antibiotic resistance (Ahmad and Khan, 2019).

The introduction of rapid, POC tests to Primary Care hold the potential to positively improve patient treatment and reduce the economic cost the healthcare systems. The study POC assay is a rapid, point-of-care diagnostic test that is designed to aid in the differentiation of bacterial and viral ARIs, with the objective to help reduce inappropriate prescriptions of antibiotics in Primary Care practices. The POC assay is designed to be used by clinicians and makes use of MxA and CRP biomarkers in capillary blood to provide qualitative data to distinguish between viral and bacterial infections. CRP however is not considered an effective biomarker to distinguish between infections solely, due to being largely nonspecific. CRP levels can be raised due to lifestyle habits such as diet, smoking and limited physical activity, that are not suggestive of infection (Young, Gleeson and Cripps, 1991). MxA is an intracellular GTPase protein that is induced by type I and type III interferons and which serves as a sensitive and specific marker for viral infection (Haller and Kochs, 2011). The rationale of the POC assay is therefore to use a combination of both biomarkers to combine the sensitivity of CRP and specify of MxA to aid in the differentiation of ARI's in Primary Care.

Early clinical studies using the POC assay at Primary Care level in the United States has proven effective as a decision-making tool. A two centre study produced a high degree of diagnostic accuracy with bacterial vs viral at 92% and viral vs non-viral at 84-87% agreement (Self et al., 2017). Complimentary to data regarding the performance of the POC assay at Primary Care, initial data suggests that the POC assay can be a vital decision-making tool, where it is uncertain if antibiotics should be prescribed (NICE, 2021). An additional feature of the POC assay would be in improving the clinical management of patients with ARI's as clinical uncertainty can lead to the inappropriate prescription of antibiotics for ARI's. The reduction in consultations and treatment of antibiotic-related adverse events could result in significant cost savings as an antibiotic stewardship method (Beck et al., 2017). However, further evaluation of the POC assay would be of great clinical significance to a Primary Care outpatient setting, including for use with patients that would benefit from antibiotics (Shirley, 2019).

### 3.0 Study Aims and Objectives

A Primary care administered POC dual marker immunoassay utilising new technologies allowing on-site “in-house” diagnosis of ARI's may reduce unnecessary antibiotic prescribing by defining the bacterial or viral source of the infection. The POC assay could be used to guide GP's patient treatment and management decisions.

The primary objective of the study is to determine whether the POC assay is useful in aiding clinicians in the decision to prescribe antibiotics (Table 1).

Primary aims	Secondary aims

 
• Use a POC assay to distinguish between bacterial and viral infection in the Primary Care setting.
 
• To assess the feasibility of using POCT to support clinician decision making in prescribing antibiotics.
 
	
 
• Produce data to evaluate usefulness of the POC assay.
 
• Compare POC assay use to other POC assays used in Primary Care.
 

**Table 1:** Primary & Secondary Study aims.

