### 4.0 Study Participants

The study population will be recruited from self-referred patients attending YCR and KHPC centres with a self-suspected acute respiratory infection (ARI). The study aims to collect a minimum of 140 participants using a pragmatic sampling regime. The feasibility study will

provide the data required to design and conduct a more detailed and statistically powered trial.

The ASPIRE study will not replace clinical judgement or expertise. Patient management actions will be based on clinical judgement independent of the POC assay results. The physician will only have access to this data after the patient has finished their consultation.

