## **6. Data collection**

The POC test result will be performed in a separate room after the consultation is over and the patient's treatment decided upon. The GP will be blinded to the study and presented an information sheet and consent form prior to the patient's consultation to agree upon these terms.

The POC assay outcome and the participant characteristics at presentation will be recorded on CRF 1. All patient identifiable data will remain at Keir Hardie and Ysbyty Cwm Rhondda Primary Care Centres. The following information will be collected:

Demographics: Age, Sex, Weight, Height

Clinical Findings, Arterial O2 Saturation, resting heart Rate, CRB, resting Respiratory Rate and (office) Blood Pressure (where available).

The CRF 1 will also record any additional tests the GP may have requested as per the standard treatment procedure such as sputum or PCT tests. CRF1 will record the final diagnosis.

CRF1 will include a tick-box to state whether the participant has agreed to participate in a follow-up call after 14 days of their initial appointment. Each participant will be asked if they would be able to conduct a short telephone call with the research student to discuss the

outcomes of the treatment. If consented, the participant will confirm this on a tick box on CRF 1 and will be asked to provide a suitable contact mode and time to call back on the follow up form. Follow up data will be recorded on CRF 2.

Participant's medical records will be reviewed at the Primary care Practice to collect data concerning follow up treatment after 14 days to determine whether patients returned for medical treatment post appointment. Patient medical records will also be used to determine the clinical judgment of the initial assessment i.e. where they prescribed antibiotics or not. The clinical judgement and course of treatment followed will then be compared to the course of treatment that would have been suggested by the POC dual marker immunoassay result.

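### The primary objective claims the assay's usefulness to prescribers, but the design, which tests after treatment is decided, can deliver only feasibility and potential impact

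*Protocol*

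**What the plan says.** Protocol section 3.0 gives the primary objective as to "determine whether the POC assay is useful in aiding clinicians in the decision to prescribe antibiotics (Table 1"). The table it cites has two primary aims. One is to tell bacterial from viral infection with the assay. The other is "To assess the feasibility of using POCT to support clinician decision making in prescribing antibiotics". Usefulness appears by name only among the secondary aims, as "Produce data to evaluate usefulness of the POC assay".

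Section 4.0 keeps the result out of patient care: "Patient management actions will be based on clinical judgement independent of the POC assay results", and "The physician will only have access to this data after the patient has finished their consultation". Section 6 fixes the order of events: "The POC test result will be performed in a separate room after the consultation is over and the patient's treatment decided upon". It also states that the GP is blinded.

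The planned comparison, in section 6, is this: "The clinical judgement and course of treatment followed will then be compared to the course of treatment that would have been suggested" by the assay. Section 1.1 adds that "The POC assay results will be compared to the participants' clinical outcomes and the physician directed treatment pathway", with record review and patient contact from 14 days. The same section describes the study as uncontrolled and observational.

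**The concern.** Whether a test aids a decision is a question about what clinicians do when they have the result, compared with what they do without it. Here the decision always comes first. The study can show that the assay would have pointed to a different treatment. It cannot show that a GP who saw the result would have acted on it, or decided better because of it.

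At stake is the headline conclusion. A team that followed the protocol exactly would have feasibility data and a rate of agreement between prescribing and the assay, and would report them under a primary objective worded as usefulness. Those planning the later powered trial could read that as evidence of benefit to prescribers. An analysis plan could not mend this, because the mismatch comes from the timing of the test and the blinding, both fixed in the protocol.

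**Working it through.** The plan has no figure to reproduce on this point. The minimum of 140 participants (section 4.0) is described as pragmatic and comes with no rate, effect size or power. The check sets the objective beside the design and then asks what can be estimated.

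**1. What the objective needs and what the design supplies**

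| Needed to show that the assay aids decisions | Supplied by the protocol |
|---|---|
| Decisions made with the result available | None: the test follows the treatment decision (section 6) |
| A clinician who can use the result | GP blinded (section 6); access only after the consultation (section 4.0) |
| Management that may respond to the result | Management independent of the result (section 4.0) |
| A comparison of decisions with and without the result | No control (section 1.1); the comparison is with a hypothetical treatment (section 6) |

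The effect on decisions can be written as

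P(prescribe, result seen) − P(prescribe, result not seen).

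The study observes the second term in all participants. For the first it observes 0 of 140, so the difference cannot be estimated at any sample size.

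**2. What can be estimated**

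Let D be the proportion of initial decisions that differ from the assay-suggested treatment, with n = 140.

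- The widest 95% half-width, at D = 0.5, is 1.96 × √(0.25/140) = 0.083, or 8.3 percentage points.
- The protocol gives no expected D. For an assumed range of 10% to 30%, the Wilson 95% intervals are:
  - 14/140 (10%): 6.1% to 16.1%
  - 28/140 (20%): 14.2% to 27.4%
  - 42/140 (30%): 23.0% to 38.0%

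That is adequate precision for a feasibility study. Outcomes and re-attendance after 14 days can be described alongside D.

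**3. Sentence against Table 1**

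The sentence would settle usefulness as the primary objective. The table only gathers data towards usefulness, and ranks it secondary. The table's second primary aim concerns the same activity, supporting the prescribing decision, but asks whether it is feasible. The difference is therefore one of claim (useful against feasible) and of rank, not of subject.

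**4. Which decision counts**

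Section 4.1 says that patients who test positive for bacterial infection may be given antibiotics, and section 4.0 lets the physician see the result after the consultation. Section 6 takes the prescribing decision from the medical records. A prescription written after release could thus be read as the initial decision and would make agreement look better than it was. The protocol does not say that only the earlier decision counts.

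**The case against.** The strongest reply is that the sentence is an umbrella and Table 1 spells it out. On that reading, useful in aiding a decision and feasible for supporting one are nearly the same idea, and the rest of the document is modest. It speaks of retrospective insight (section 2.1), data for a later powered trial (section 4.0) and possible future interventional use (caption to Figure 2, Appendix 1). Much of this stands. A reader might infer that the protocol sets two rival primary objectives. The overlap with the second primary aim does not support that, and the conflict with the table is only partial. The modest passages do not rescue the sentence, though. They show that it is the part out of line.

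A second reply is that discordance and follow-up do bear on usefulness. Near-total agreement, for instance, would suggest that the assay has little room to change prescribing. That is right, and it is why potential impact is a proper objective. It would be too strong to infer that the study says nothing about usefulness.

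A reader might also take the statement in section 4.1 as proof that results guide treatment here. It does not fit sections 4.0 and 6, and no comparison of decisions before and after release is planned.

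**Conclusion.** The point holds for the wording of the primary objective: it claims clinical utility, and the design yields feasibility and potential impact. In size, 0 of at least 140 initial decisions are informed by the result, while the discordance proportion can be estimated to within 8.3 points at worst. The precision figures assume that all 140 participants have both a recorded initial decision and a usable assay result, and that a rule turns each result into a suggested treatment. The 10% to 30% range is an assumption. The main conclusion depends on none of these.

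The data remain sound, so this is a correction to the claim and not to the design. Three further inferences are not supported:

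- That the blinding is a fault. It protects the initial decision from the result and is defensible.
- That discordance can be split into GP error and assay error. This would need assumptions about true aetiology, accuracy in this population and independence of errors that the protocol does not supply.
- That the secondary aim on other POC assays should be deleted for want of a comparator. The pathway figure is not shown, and its notes mention POC test systems in the plural.

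**What to change.** 1. Restate the primary objective in section 3.0 along these lines: to assess whether the assay can feasibly support prescribing decisions in primary care, and to estimate its potential impact as the proportion of initial prescribing decisions, made before the result is available, that differ from the assay-suggested treatment, with a 95% CI.
2. Add the same potential-impact wording to Table 1 and keep both existing primary aims, so that sentence and table agree.
3. State that only the decision made before release of the result counts as the initial decision, whatever is prescribed later under section 4.1.
4. Describe outcomes and re-attendance after 14 days alongside the proportion, and leave any effect on decisions to the later powered trial.
5. Keep the blinding.

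The cost is a more modest primary claim. Section 6 already collects the treatment decision, the assay result and the follow-up, so no extra patients, tests or visits are needed. Item 3 may need one dated prescription field on the CRF if there is none already; the CRFs are not shown.

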### 4.0 Study Participants

The study population will be recruited from self-referred patients attending YCR and KHPC centres with a self-suspected acute respiratory infection (ARI). The study aims to collect a minimum of 140 participants using a pragmatic sampling regime. The feasibility study will

provide the data required to design and conduct a more detailed and statistically powered trial.

The ASPIRE study will not replace clinical judgement or expertise. Patient management actions will be based on clinical judgement independent of the POC assay results. The physician will only have access to this data after the patient has finished their consultation.

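### GP access to the assay result is barred only until the consultation ends, so the follow-up outcomes compared with the assay can be influenced by knowledge of the result

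*Protocol*

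**What the plan says.** **Access and independence.** Section 4.0 (Study Participants) states: "Patient management actions will be based on clinical judgement independent of the POC assay results". The next sentence sets the access rule: "The physician will only have access to this data after the patient has finished their consultation".

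**Timing of the assay.** Section 6 (Data collection) has the test "performed in a separate room after the consultation is over and the patient's treatment decided upon". It adds: "The GP will be blinded to the study and presented an information sheet and consent form prior to the patient's consultation". The GP agrees to those terms, but no end to the blinding is given.

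**Use of a positive result.** Section 4.1 says that patients who test positive for bacterial infection can be prescribed antibiotics along the NICE pathway.

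**What the assay is compared with.** Section 1.1 (Study Setting): "The POC assay results will be compared to the participants' clinical outcomes and the physician directed treatment pathway", from medical records and from patient contact starting 14 days after the visit. Section 6 adds a review of records at the practice "to determine whether patients returned for medical treatment post appointment", and a comparison of the GP's judgement and treatment with the course that the assay would have suggested. Section 7 analyses the assay data together with medical records and clinical outcome, and sets a 0.05 significance level for comparing diagnostic test results.

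**Diagnosis.** Section 6 also says "CRF1 will record the final diagnosis", without a time point.

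**The concern.** An assay can be judged against later outcomes only if its result did not help to produce them. Here some of those outcomes, notably return visits and later treatment, are partly decisions of the practice that may hold the result.

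Take a participant sent home without antibiotics whose assay then reads bacterial. If the GP sees the result and recalls the participant, the record shows a return and perhaps a later prescription, which would look like agreement between assay and clinical course. If the GP instead arranges treatment early and a return is averted, the same record would hide a true relation.

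These participants, in whom GP and assay disagree, carry most of the information on whether the assay could have helped, which is the primary objective in section 3.0. Section 4.0 also says the study is to supply data for designing a powered trial, so a contaminated association could be carried forward. An analysis plan could not repair this later if nobody recorded when the practice saw the result.

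**Working it through.** No stated figure depends on this point. The 140 is a pragmatic minimum without rates or power behind it, so there is nothing to reproduce. The check is the order of events, followed by an illustration.

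**Order of events**

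| Step | Could the GP know the result? | Source |
|---|---|---|
| Consultation and treatment decision | No; the assay has not been run | Section 6 |
| Finger prick and assay, separate room | Not yet | Sections 5 and 6 |
| From the end of the consultation onwards | Yes, access is no longer barred | Section 4.0 |
| Return visits and follow-up treatment | Yes | Sections 1.1 and 6 |
| Record review and call, from 14 days | Yes | Sections 1.1 and 6 |

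The comparison of the index decision with the assay-suggested course rests on the first row and is protected. The comparison with return visits, follow-up treatment and clinical outcome rests on the last rows and is not.

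**Do other statements close the gap?** The independence sentence in section 4.0 has no time limit, but no mechanism supports it beyond the consultation. The blinding statement in section 6 has no end. Section 4.1 points the other way by allowing a positive result to lead to a prescription. These passages are not aligned.

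**Illustration (every rate is assumed).** Suppose the assay has no true relation to return visits. Let *b* be the return rate without contamination (10–20%), *u* the share of assay-positive participants without an initial antibiotic (30–50%), and *f* the share of those recalled because the result was seen. The observed return rate in positives is

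*b* + (1 − *b*) × *u* × *f*, against *b* in the others.

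- *f* = 0: the rate is *b* and the ratio is 1.
- *f* = 25%: lowest ratio 0.20 + 0.80 × 0.30 × 0.25 = 0.26, and 0.26/0.20 = 1.3; highest ratio 0.10 + 0.90 × 0.50 × 0.25 = 0.2125, and 0.2125/0.10 = 2.1.
- *f* = 50%: lowest ratio 0.20 + 0.80 × 0.30 × 0.50 = 0.32, ratio 1.6; highest ratio 0.10 + 0.90 × 0.50 × 0.50 = 0.325, ratio 3.3.

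With 20–30% of 140 assay-positive (28 or 42 against 112 or 98), a two-sided comparison of return rates at 0.05 would be significant with probability 12–44% at *f* = 25% and 29–87% at *f* = 50% (normal approximation), against about 5% at *f* = 0.

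**Opposite direction.** If seeing the result instead leads to treatment without a visit, and that averts the return, the rate in positives is *b* × (1 − *u* × *f*). With *b* = 0.20, *u* = 0.50 and *f* = 0.25 this is 0.20 × 0.875 = 0.175, below the 0.20 in the others. The sign therefore depends on what the practice does.

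**The case against.** The strongest reply is that the protocol already forbids the harm. Section 4.0 says without time limit that management is independent of the assay, and the GP agrees to blinding terms under section 6. On that reading a recall prompted by the result would breach the protocol, and the triggering rate would be zero. The two sentences in section 4.0 need not conflict, since one governs use of the result and the other access to it. The patient-pathway figure and the GP information sheet are not visible and might state a release date. The study is an uncontrolled feasibility study, and the comparison closest to its prescribing objective is protected.

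Much of this stands, and it rules out several stronger readings that a reader might infer:

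- *Results are routinely released as the consultation ends.* Section 4.0 gives an earliest time for access, not a release schedule.
- *The index prescribing comparison is contaminated.* Section 6 excludes this by running the assay after treatment is decided.
- *The bias favours the assay.* Either direction is possible, as shown above.
- *The diagnosis on CRF 1 is contaminated.* Its timing is unstated, but CRF 1 records characteristics at presentation, and no passage names this diagnosis as the assay's comparator.

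What the reply does not remove is that independence after the consultation rests on a declaration, that section 4.1 provides a route by which a positive result may change treatment, and that nothing would record whether this happened.

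**Conclusion.** The point holds as a gap in study conduct. On the visible text, knowledge of the assay result can influence the return visits, follow-up treatment and clinical outcomes with which the assay is compared. Independence is secured for the index consultation only.

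The size cannot be determined from the documents. The ratios above rest wholly on assumed rates and run from none (ratio 1, if the independence sentence is kept in practice) to marked distortion if recall is common. They show that the issue is not negligible at this sample size, not that it will occur. The conclusion assumes that the pathway figure and the GP information sheet, which are not visible, contain no later release rule.

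It deserves correction because it is cheap now and the missing dates may be unrecoverable later.

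**What to change.** 1. Reconcile sections 4.0, 4.1 and 6 on who may see the result, when, and whether it may affect management. The clinical rule is for the sponsor and investigators to decide.
2. State that independence is secured only for the index consultation, unless access is restricted through the 14-day review.
3. Enter the GP's diagnosis and prescribing decision on CRF 1, with the time, before the finger prick.
4. For every participant, record whether and when the treating practice first saw the result, and any action taken because of it. Use CRF 1 or the record-review form. CRF 2 alone is unsuitable: section 6 introduces it with the consented telephone call, so the date could be missing for those who decline.
5. Report follow-up events by whether they were prompted by, or occurred after, access to the result. Keep all events in the main description, and interpret the assay-outcome comparison as possibly contaminated where access came first.
6. Do not restrict the comparison to events not preceded by access. A GP may open the result because the patient has returned, so that restriction would select on the outcome; with early access it would also discard most follow-up events, including spontaneous returns.

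The cost is protocol wording, a few extra CRF fields and a more cautious conclusion from the follow-up comparison.
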